6.14.7 Assessment of Cognitive Impairment

The DSST will be used to measure cognitive impairment due to Scop HBT. The raw score will be calculated from the difference in total number of trials attempted and the number of trials incorrect. Summary statistics for raw DSST scores (mean, median, min, max, standard deviation, 95% confidence intervals) will be presented over time by dose level. The proportion of individuals with declines in raw scores between baseline and 48 hours and baseline and Day 8 will be compared between active placebo and active Scop HBT using a Fisher's Exact Test. This test will be conducted once for all participants receiving active Scop HBT and all participants receiving placebo.

In addition, individual changes in DSST scores between baseline and 48 hours and SD 8 will be compared between each dosage cohort and placebo and for all active dosages and placebo. Equation 5 presents the model that will be used to compare DSST scores by cohort,

$$G(Y_i) = \beta_0 + \beta_1 \times I(D_i = 1) + \beta_2 \times I(D_i = 2) + \beta_3 \times I(D_i = 3) + \beta_4 \times I(D_i = 4) + \beta_5 \times I(D_i = 5) + \varepsilon_i \quad (5)$$

where $Y_{i,}$ is the change in DSST scores at 48 hours or SD 8, D_i is the dosage level for participant i ($1=0.005, 2=0.007, 3=0.011, 4=0.014, 5=0.021 \text{ mg/kg}$), β_0 is the change in DSST scores for placebo participants, and ε_i is the error term for each participant i . Wald tests will be used for the null hypotheses of no differences between active Scop HBT and placebo: $\beta_1 = 0, \beta_2 = 0, \beta_3 = 0, \beta_4 = 0, \beta_5 = 0$.

Equation 6 shows the model that will be used to test the null hypothesis of no differences between all levels of active Scop HBT compared to placebo

$$G(Y_i) = \beta_0 + \beta_1 \times I(D_i \in \{1,2,3,4,5\}) + \varepsilon_i \quad (6)$$

A Wald test will be used to test the null hypothesis that there are no significant differences in the change in DSST scores between active and placebo Scop HBT ($\beta_1 = 0$) in Eq. 6.

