12.1.2. Safety Analyses

Safety analysis will include data collected from the safety analysis set. DLT and AE data will be coded using the current MedDRA version at the time of study setup, listed individually (including intervention and outcome), and summarized by system organ class and preferred terms within a body system for each treatment group. Data will be summarized by both event (counting each event regardless of subject) and by subject (counting only one event within each system organ class or preferred term). Serious and/or unexpected AEs will also be discussed on a case-by-case basis.

Changes in pulse rate, systolic and diastolic blood pressure, weight, and respiratory rate will be summarized (mean, median, minimum, maximum, standard deviation) by dose level and time point. Clinical laboratory assessment results will be presented.

Upper bounds of 80% confidence intervals of the true probability of events (extreme DLTs, non-extreme DLTs, and severe AEs) will be estimated from the number of events in each cohort using the Pearson-Clopper method.

Descriptive statistics of BPRS, C-SSRS, DSST, RASS (if conducted), and injection site VAS scores (mean, median, standard deviation, minimum, and maximum) will be presented for each dose level and time point.

Changes in the BPRS score (6 hours, 48 hours, and 8 days) from baseline will be compared between placebo and active dose levels using ANOVA models for each time point. The null hypothesis of no difference between placebo and the active dose will be tested for each dose level using a one-sided alternative hypothesis of higher increases among the participants receiving the active drug than among the placebo group.

Participants have C-SSRS scores of zero at baseline. The proportion of individuals having any increase in their C-SSRS score from zero will be compared for each drug dosage level to the placebo group using Fisher's exact test.

The DSST will be conducted at screening, Day -1, Day 3, and Day 8. Changes from baseline (Day -1) will be compared between placebo and active dose levels using ANOVA models for each time point. Placebo control will help to exclude any remaining practice effects or changes

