unrelated to the study drug. The null hypothesis of no difference in DSST scores between active Scopolamine and placebo will be tested for each dose level using a one-sided alternative hypothesis of more negative changes in DSST scores among participants receiving the active drug than among the placebo group. A pooled analysis will compare all Scopolamine dosage levels to placebo. Individual participants' DSST scores will be presented by study day, and persistent declines in scores at Day 3 or Day 8 will be noted.

Frequencies of severity (None, Mild, Moderate, Severe, Potentially Life Threatening) from injection site assessments performed by clinicians will be summarized by type (pain, tenderness, erythema/redness, induration/swelling) and time point by dosage group. Semi-log graphs of mean VAS scores will be plotted (VAS score vs. log-time since injection). Differences between placebo and active drug injection site VAS scores will be compared statistically by dosage level using 3 different ANOVA models corresponding to the first hour, next 4 hours, and 8-48 hours after injection. A Wald test with a one-sided alternative will be used.

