3.4 STUDY POPULATION

[figure not shown]
The study will include up to 60 male and female volunteers, 18 to 55 years of age, who will be enrolled in 5 dosing groups (cohorts) of 8 to 12 participants each. The actual number enrolled in the study will be determined by the safety responses noted during the study. Each of the 5 cohorts will include at least 3 male and 3 female participants enrolled among the first 8 participants in the cohort to ensure that at least 1 male and 1 female subject in each dosing group receive active drug. Each cohort will include 6 to 9 individuals receiving active and 2-3 receiving placebo doses (total of 30-45 active and 10-15 placebo).

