5.1.9 Cognitive Assessment

The digit symbol substitution test (DSST) will be used to measure cognitive impairment associated with Scop HBT. Study staff are experienced at performing the test, which typically takes 8 minutes to complete. The DSST will be administered at screening, at SD -1 (baseline), 48 hours after injection (SD 3), and at the SD 8 follow-up visit. The DSST conducted at screening is intended to reduce practice effects. If the PI or designee determines a subject is incapable of engaging in the DSST at one or more time point(s), the reason(s) why the DSST assessment(s) could not be done will be documented by time point in the source documentation.

The DSST will be used test for persistent cognitive impairment associated with Scop HBT at the individual and population levels. Differences in raw scores (number of correct pairings in 120 seconds) between baseline and SD 3 and SD 8 will be presented individually in listings. The

² Posner K, Brown GK, Stanley B, Brent DA, Yershova KV, Oquendo MA, Currier GW, Melvin GA, Greenhill L, Shen S, Mann JJ (2011). *The Columbia-Suicide Severity Rating Scale: Initial Validity and Internal Consistency Findings from Three Multisite Studies with Adolescents and Adults*. American Journal of Psychiatry 168(12): 1266-77.

persistent effects of Scop HBT on cognition will also be assessed through comparison of within-person changes in scores from baseline between active and placebo groups

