5.3 COVARIATES

In general, covariates are not applicable for this study, with the exception of PK analysis. The influence of the dose of Scopolamine will be evaluated in various analyses including the PK dose-response relationship, with sex included as a covariate. Sex is valid as a covariate in models of PK parameters based on plasma concentrations, as males typically have higher plasma volumes per unit body mass than females.

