6.3 HYPOTHESES AND DECISION RULES

As the objective of this study is to characterize the safety and tolerability of escalating doses of Scop HBT, three sets of safety endpoints will be compared statistically between placebo and active dosing groups. Some PK parameters will also be compared statistically across dose levels. Table 7 describes the hypothesis testing pre-specified in the statistical analysis.

The null hypothesis of no worse scores for Injection Site VAS (pain, itching, tingling, numbness); change in BPRS Score (6 hours, 48 hours, 8 days); change in DSST (48 hours, 8 days); and C-SSRS (SD 8) between dose levels of active Scop HBT and placebo will be tested statistically using a one-sided alternative of worse (higher for C-SSRS, VAS, and BPRS, lower for DSST scores for Scop HBT vs. placebo). Each dose level will be tested against the same placebo group (all participants receiving placebo). Methods for analysis of neuropsychiatric scales and injection site reactions are described in Sections 6.13.4 [6.14.6](#) and [6.14.8](#), respectively.

For PK parameters, variation across doses will be tested for T_{max} , $t_{1/2}$, V_d/F , Cl_F , and MRT against the null hypothesis of no difference across doses. A joint significance test (1 test per parameter) will be used.

Dose-proportionality will be tested using the dose-normalized parameters $C_{max}/Dose$ and $AUC_{\infty}/Dose$. A likelihood ratio test will be used for testing the joint null hypothesis of equivalence across all doses using a two-sided alternative. Each dose level will also be tested against the next dose level using a two-sided test. The methods for analysis and hypothesis testing are described in Section - [6.15](#). A total of 110 hypothesis tests will be performed. Procedures for multiple comparisons are detailed in Section [6.8](#).

Table 7: Pre-Specified Hypothesis Tests

Drug Characteristic	Null Hypothesis	Relevant Endpoints [Count]	Number of Comparisons Per Parameter	Total Number of Hypothesis Tests
Safety	Equivalence with Placebo	Injection site VAS (pain, itching, tingling, numbness) x (10-45 minutes, 1-5 hours, 8-48 hours) [12] Change in BPRS score from baseline (6 hours, 48 hours, SD 8) [3] Change in DSST scores from baseline (48 hours, SD 8) [2]	5 (Each dose level vs. Placebo)	90

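### The DSST change-score models omit Day -1 DSST as a covariate: a valid analysis that gives up a modest, correlation-dependent amount of precision

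*SAP*

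**What the plan says.** - **Outcome and model.** SAP 6.14.7 states that "individual changes in DSST scores between baseline and 48 hours and SD 8 will be compared between each dosage cohort and placebo". In Equation 5 the outcome "is the change in DSST scores at 48 hours or SD 8". The right-hand side holds an intercept and five dose indicators. Equation 6 replaces these with one any-active indicator. Wald tests are applied to the coefficients.
- **Protocol.** Section 12.1.2 agrees: "Changes from baseline (Day -1) will be compared between placebo and active dose levels using ANOVA models for each time point". It tests against a "one-sided alternative hypothesis of more negative changes in DSST scores among participants receiving the active drug" than on placebo.
- **Covariates.** SAP 5.3: "In general, covariates are not applicable for this study, with the exception of PK analysis".
- **Baseline is available.** SAP 5.1.9: "The DSST will be administered at screening, at SD -1 (baseline), 48 hours after injection (SD 3), and at the SD 8 follow-up visit". The screening administration serves as practice, and DSST plays no part in eligibility.
- **Sizes.** SAP 3.4: "Each cohort will include 6 to 9 individuals receiving active and 2-3 receiving placebo doses (total of 30-45 active and 10-15 placebo". SAP 6.3: "Each dose level will be tested against the same placebo group (all participants receiving placebo".

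Neither document enters Day -1 DSST as a covariate. Neither gives a DSST standard deviation, effect size, correlation or power.

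**The concern.** A change score uses the baseline, but with its coefficient fixed at 1. When the baseline to follow-up correlation is below 1 and the spread is similar at both times, the best-fitting slope is below 1. The change score then subtracts too much. Two things follow:

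- The residual variance is larger than it need be.
- A dose group that happens to start low tends to drift upward relative to placebo. In a one-sided test for decline, this can hide part of a real effect. Because all doses share one placebo group, a chance deviation in the placebo baseline enters every dose contrast.

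The DSST is the instrument assigned to detect persistent cognitive effects. SAP Table 7 gives it 10 per-dose tests of change (2 time points x 5 doses), 2 pooled tests of change and 2 pooled tests of the proportion declining.

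**Working it through.** **The plan's own figure.** The only sample-size arithmetic, in SAP 3.5, concerns event detection: 1 - (1 - 0.235)^6 = 0.7996, which reproduces the stated 80%. It does not bear on DSST precision, so there is no planned figure to compare with.

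**Inputs.** From SAP 3.4 and 6.3, the contrasts run from 6 v 10 (N = 40) to 9 v 15 (N = 60). Equation 5 has six parameters, so the error df are 40 - 6 = 34 to 60 - 6 = 54. Assumed, because the documents are silent: equal SD s before and after, and rho from 0.5 to 0.95.

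**Formulas.**
- Change score: variance 2s²(1 - rho).
- Baseline-adjusted: variance s²(1 - rho²).
- Large-sample ratio, adjusted to change score: (1 + rho)/2.
- Estimating the slope multiplies the adjusted variance by 1 + 1/(df - 2). This is 1 + 1/32 = 1.031 at N = 40 and 1 + 1/52 = 1.019 at N = 60.

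**Variance ratio and excess SE of the planned analysis (Equation 5).**

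| rho | (1 + rho)/2 | Ratio, N = 40 | Ratio, N = 60 | Variance cut | Excess SE |
|---|---|---|---|---|---|
| 0.5 | 0.75 | 0.773 | 0.764 | 23-24% | 14% |
| 0.7 | 0.85 | 0.877 | 0.866 | 12-13% | 7% |
| 0.8 | 0.90 | 0.928 | 0.917 | 7-8% | 4% |
| 0.9 | 0.95 | 0.980 | 0.968 | 2-3% | 1-2% |
| 0.95 | 0.975 | 1.005 | 0.994 | none to 0.6% | about 0 |

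Simulation of Equation 5 with and without baseline (20,000 runs per setting, rho 0.5 to 0.9) gave ratios within 0.004 of these. For Equation 6 with 30 v 10, the ratios are 0.771, 0.874, 0.925 and 0.976 at rho 0.5, 0.7, 0.8 and 0.9.

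**Power for a drop of 0.5 SD** (illustrative effect, one-sided 0.05), change score v adjusted:

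| rho | 6 v 10 | 9 v 15 |
|---|---|---|
| 0.5 | 24.3% v 28.6% | 31.8% v 38.0% |
| 0.7 | 33.7% v 36.8% | 44.7% v 49.2% |
| 0.8 | 44.3% v 46.5% | 58.2% v 61.3% |
| 0.9 | 68.3% v 69.1% | 83.5% v 84.5% |

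**Break-even rho** = 2/[1 + 1/(df - 2)] - 1.
- All five cohorts: 0.939 (df 34) to 0.962 (df 54).
- Three cohorts of 8: N = 24, four groups, df 20; 2 x 18/19 - 1 = 0.89.
- Two cohorts: N = 16, three groups, df 13; 2 x 11/12 - 1 = 0.83.
- One cohort: N = 8, two groups, df 6; 2 x 4/5 - 1 = 0.60.

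**Chance imbalance.** The SE of a baseline mean difference is sqrt(1/6 + 1/10) = 0.52 SD, or sqrt(1/9 + 1/15) = 0.42 SD. A difference above 0.5 SD in either direction therefore arises in about 33% (6 v 10) or 24% (9 v 15) of single contrasts. Given an imbalance d, the change-score contrast is off by (1 - rho)d. For d = 0.5 SD this is 0.25 SD at rho 0.5, 0.15 at 0.7 and 0.10 at 0.8.

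**Unequal SDs.** With s1 before and s2 after, the large-sample gain is (s1 - rho x s2)². At rho 0.8 it vanishes if s2 = 1.25 x s1, and it is larger if s2 is smaller than s1.

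**The case against.** The strongest reply is that nothing here is wrong. Protocol and SAP agree, the test keeps its error rate under randomisation, and baseline is used through the change itself. All of that stands. A reader might infer that the plan ignores baseline or yields a biased comparison. It does neither: the error (1 - rho)d is conditional on the imbalance that happens to occur, and it averages to zero over randomisations.

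A second reply is that the gain is probably small. A practice run, the same test and retests at 48 hours and Day 8 all suggest a high rho, and the better baseline predicts follow-up, the less an estimated slope adds. This too stands as a judgement, although the documents do not settle rho.

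Third, Protocol 12.2 warns that enrolment may stop well short of 40-60. The break-even figures show that adjustment could then lose precision. This stands and shapes the fix.

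Fourth, the consequence is limited. SAP 6.1 relies mainly on description, SAP 6.8 treats the trial as exploratory with a false discovery rate of 0.20, individual DSST changes are listed, and Protocol 12.3 and SAP 6.7.2 keep statistical tests out of halting and termination decisions. This bears on severity. It does not remove the point.

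**Conclusion.** The point holds as a minor efficiency improvement. Under equal SDs and five completed cohorts, the planned model costs about 14% in SE at rho 0.5, 7% at 0.7, 4% at 0.8 and 1-2% at 0.9, and nothing above about 0.94-0.96. The true position in that range is unknown. Early stopping lowers the break-even rho to about 0.89, 0.83 or 0.60 after three, two or one cohorts of 8. SAP 6.11 also censors DSST after rescue medication, which could reduce the df further.

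Three stronger readings are not supported:
- That adjustment always wins, or saves the full 25%, 15%, 10% and 5% given by (1 + rho)/2. That ratio omits the cost of estimating the slope.
- That the contrasts rest on 6-9 people alone. Placebo is pooled to 10-15, and Equation 5 pools its error over all participants.
- That BPRS needs the same change. It has 24 items with a minimum score of 1 each, and eligibility caps the total at 25, so there is almost no baseline variation to adjust for.

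**What to change.** Before unblinding:

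1. Add Day -1 DSST as a covariate in Equations 5 and 6, with the same one-sided Wald tests of the dose coefficients. Change or follow-up score may be the outcome; the dose coefficients are then identical.
2. Amend SAP 5.3 to allow this covariate, and Protocol 12.1.2 to match.
3. Carry the covariate into the SAP 6.10 fallback for DSST, where the two-sample bootstrap statistic has no place for it. One way is to bootstrap the baseline-adjusted coefficient; Protocol 12.5 already refers to bootstrap standard errors for coefficients.
4. Keep the unadjusted change-score model as a sensitivity analysis outside the 110 counted tests. State now that it becomes the main analysis if the trial stops after one or two cohorts, so that the choice depends on cohorts completed and not on the data.

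The cost is one degree of freedom out of 34-54 if all cohorts complete, and no new data. The amendment is small, but SAP 6.2 requires a revised protocol with sponsor, statistician and ethics approval for a change to a protocol-specified analysis. The number of main tests does not change.

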6. STATISTICAL METHODOLOGY AND ANALYSES

6.1 GENERAL CONSIDERATIONS

The first and second objective of this study will primarily be addressed through descriptive statistics of safety and PK data. Hypothesis testing and interval estimation will be limited. Specific hypotheses are detailed in 6.3 and interval estimation in 6.4. All data analyses and statistical testing will be conducted using SAS Version 9.4 or Stata version 15 or higher.

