6.8 ADJUSTMENT FOR MULTIPLE COMPARISONS

Section [6.3](#) specifies the hypotheses to be tested in this Phase 1 trial of the safety and pharmacokinetics of IM injection of Scop HBT. Given the large number of hypothesis tests, the Benjamini-Hochberg method will be used to determine statistical significance. As this trial is exploratory, a relatively high false discovery rate (FDR), the proportion of significant findings that are spurious, will be used. For this study, the FDR will be set at 0.20. The choice of a high FDR prevents rejecting marginally significant findings, which may provide important information about the drug's safety and pharmacokinetic properties. With 110 tests and an FDR of 0.20, the threshold for statistical significance for the five lowest p-values will be 0.0018,

0.0036, 0.0055, 0.0073, and 0.0091. Statistical significance of tests will be noted using at the alpha = 0.05 level as well as through the Benjamini-Hochberg method. Study sponsors should note that one-in-five significant findings obtained through this process are expected to be spurious.

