6.14.6 Neuropsychiatric Scales

Descriptive statistics (mean, standard deviation, minimum, maximum, median) of scores on the neuropsychiatric status assessments (BPRS and C-SSRS) will be presented for each timepoint by dosing group (placebo, 0.005, 0.007, 0.011, 0.014, 0.021mg/kg).

As the RASS will only be used if general agitation or sedation are reported, the number of participants with RASS performed, the reason for performance of the RASS, the time since injection when the RASS was administered, the RASS score, the resulting action taken (e.g., rescue drug administered, resolved or unresolved) will be presented by dose group and overall.

Signal neuropsychiatric events defined as DLTs (BPRS ≥ 40 or item score ≥ 4 at 48-hour post-dose evaluation) or symptoms (e.g., delirium, paranoia, and/or hallucinations) defined as adverse events will be noted and the affected participants' BPRS, C-SSRS, and RASS (if applicable) scores will be presented at each time point in relation to the determination of the event.

Change in BPRS scores from baseline (when BPRS≤25) will be compared for each dose level to placebo. Each time-point will be modeled separately. Changes in BPRS scores will be compared between each dose and the placebo group using a Wald test of coefficients from ANOVA.

Change in C-SSRS scores at SD 8 (from a baseline of zero) will be assessed. The proportion of individuals having a change in score from zero will be compared for each drug dosage level to the placebo group using Fisher's exact test. Scores for all participants receiving active Scop HBT will be compared to those receiving placebo.

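### Outside a bootstrap fallback, BPRS and DSST change is compared with placebo by hypothesis tests alone, with no confidence limit on the difference, so a non-significant result would not show how much worsening remains possible.

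*SAP*

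**What the plan says.** **BPRS.** SAP 6.14.6: "Changes in BPRS scores will be compared between each dose and the placebo group using a Wald test of coefficients from ANOVA". The time points (6 h, 48 h, Day 8) are modelled separately. The descriptive output is mean, SD, minimum, maximum and median by dosing group.

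**DSST.** SAP 6.14.7: "Wald tests will be used for the null hypotheses of no differences between active Scop HBT and placebo", applied to the five dose coefficients in Eq. 5 and to one pooled-active coefficient in Eq. 6, at 48 h and Day 8. Fisher's exact test compares the proportion with a decline, all active against all placebo. The 95% confidence intervals listed there are for raw scores within each dose level.

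**Hypotheses.** SAP 6.3 opens with "The null hypothesis of no worse scores for Injection Site VAS (pain, itching, tingling, numbness); change in BPRS Score" and continues through DSST and C-SSRS; the set "will be tested statistically using a one-sided alternative of worse". The comparator is all placebo participants together. Table 7 labels the same safety null as equivalence with placebo, and no margin is given.

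**Intervals.** SAP 6.1: "Hypothesis testing and interval estimation will be limited". It sends interval estimation to 6.4, which covers DLTs and SAEs. SAP 6.10 mentions confidence intervals under a bootstrap used when normality and lognormality both fail, and it does not name the quantity.

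**Error rates.** SAP 6.8: "For this study, the FDR will be set at 0.20" over 110 tests, and "Statistical significance of tests will be noted using at the alpha = 0.05 level as well as through the Benjamini-Hochberg method".

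**Numbers.** SAP 3.4: "Each cohort will include 6 to 9 individuals receiving active and 2-3 receiving placebo doses (total of 30-45 active and 10-15 placebo").

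**The concern.** Characterising safety and tolerability is a primary objective. SAP 5.1.9 gives the DSST the task of detecting persistent impairment in individuals and in the population, and assigns part of that task to the comparison of within-person change between active and placebo. Protocol 12.1.2 explains why placebo is needed: it helps to exclude remaining practice effects.

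For that comparison the main planned result is a p-value. With 6 to 9 participants per dose, a p-value above the threshold says little about how much worsening the data still allow. The Table 7 label makes it easier to read such a result as equivalence. A difference with a confidence limit would show what has and has not been excluded.

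SAP 6.4 already works this way for DLTs: no events among 6 participants is reported as an upper bound of 0.32 and not simply as zero. The scales get no counterpart.

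**Working it through.** **The plan's own figures first.**
- SAP 3.5: 1 − (1 − 0.235)^6 = 0.80, as stated.
- SAP 6.4: upper 80% bound for 0 of 6 is 1 − 0.10^(1/6) = 0.32, as stated.
- SAP 6.8: first Benjamini-Hochberg threshold is 0.20/110 = 0.0018, as stated.

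None of these concerns BPRS or DSST. Protocol 12.2 says that no formal sample size computation was done.

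**Inputs.** Active per dose 6 to 9, placebo 10 to 15, active in total 30 to 45 (SAP 3.4); one-sided tests (6.3); alpha 0.05 (6.8). Error df are participants minus model parameters: 40 − 6 = 34 and 60 − 6 = 54 for Eq. 5; 40 − 2 = 38 and 60 − 2 = 58 for Eq. 6. The documents give no SD or effect size, so worsening is in SD units of the change score. 0.5 SD is an assumption, with a range shown below.

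**Formulas.** SE in SD units = sqrt(1/n1 + 1/n2). Non-centrality = 0.5/SE. Miss rate = P(noncentral t < t0.95,df). Limit distance = t0.95,df × SE.

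| Comparison | df | SE | Non-centrality | Miss rate, 0.5 SD | Limit beyond estimate |
|---|---|---|---|---|---|
| Per dose, 6 v 10 | 34 | 0.516 | 0.97 | 76% | 1.691 × 0.516 = 0.87 SD |
| Per dose, 9 v 15 | 54 | 0.422 | 1.19 | 68% | 1.674 × 0.422 = 0.71 SD |
| Pooled DSST, 30 v 10 | 38 | 0.365 | 1.37 | 62% | 1.686 × 0.365 = 0.62 SD |
| Pooled DSST, 45 v 15 | 58 | 0.298 | 1.68 | 49% | 1.672 × 0.298 = 0.50 SD |

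A simulation of 100,000 trials at 6 v 10 gave power 24.1%, against 24.3% from the formula.

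**Other effect sizes, per dose.**

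| True worsening | Miss rate, 6 v 10 | Miss rate, 9 v 15 |
|---|---|---|
| 0.25 SD | 88% | 86% |
| 0.5 SD | 76% | 68% |
| 0.75 SD | 59% | 46% |
| 1.0 SD | 40% | 24% |
| 1.5 SD | 11% | 3% |

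Per dose, 80% power needs 1.31 SD (6 v 10) or 1.06 SD (9 v 15).

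**Multiplicity.** At 0.0018 the miss rate for 0.5 SD is 98% at 6 v 10. That threshold applies to the smallest p-value only; later ones are looser, and results at 0.05 are also reported.

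**Rescue medication.** SAP 6.11 censors BPRS and DSST data after rescue. If two of six at a dose were lost this way (an illustration), 4 v 10 gives a miss rate of 79%.

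**The case against.** **Tests are not the whole safety assessment.** A reader might infer that BPRS and DSST safety is judged only by these tests. The documents do not support that. SAP 6.1 makes description primary, BPRS is summarised by dose and time point, affected participants' scores are shown around each signal event, DSST changes are listed individually, and Protocol 12.1.2 notes persistent declines. The DSMB uses no statistical tests. This objection stands, but none of those outputs bounds the group-level difference from placebo.

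**Persistent BPRS harm already has a bound.** An item score of 4 or more, or a total of 40 or more, at 48 h is a nonextreme DLT, and 6.4 gives an upper limit for nonextreme DLTs. That is correct. It bounds the probability of such an event in an individual. It does not bound a mean shift, does not apply at 6 h or Day 8, and has no DSST counterpart.

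**The bootstrap may supply intervals.** Entry requires a BPRS total of 25 or less on 24 items whose lowest score is 1, so baseline is 24 or 25. Change scores may well be non-normal, the 6.10 route may be used, and normal-theory power is only a guide for BPRS. This stands in part: 6.10 is conditional and does not say that the interval is for the difference. The table shells are a separate document that was not available.

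**SD units may be small in points.** If the SD of BPRS change were 2 to 5 points (an assumption), 0.87 SD would be about 1.7 to 4.4 points, against at least 15 points from baseline to the DLT total. So a clinically large worsening cannot be asserted here, and the difference should be reported in points.

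**No one says a null result means safe.** A reader might infer that the plan will conclude the drug is no worse than placebo, or that null results are likely at every dose. No section draws that conclusion, and SAP 6.8 calls the trial exploratory. Protocol 7.3.2 expects CNS effects plain enough to unblind staff, so a null BPRS result at 6 h cannot be presumed. The risk lies in how a null result might be read, and the Table 7 label adds to it.

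**Conclusion.** The concern holds as a reporting gap. For change in BPRS and DSST, the inference against placebo consists of one-sided Wald tests plus, for DSST, Fisher tests of decline. Outside the conditional bootstrap, no limit on the difference is planned.

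Under the stated assumptions (0.5 SD, all five cohorts completed, unadjusted one-sided 0.05, normal theory), a per-dose test misses the worsening about two-thirds to three-quarters of the time, and the pooled DSST test about half to three-fifths of the time. With an observed difference of zero, no single dose would exclude a 0.5 SD worsening. The pooled DSST comparison would only just reach that point, at full expansion. Cohorts stopped early or rescue censoring would make these figures worse.

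The documents do not support saying that safety rests on these tests alone, or that the plan claims absence of harm. They do support saying that a non-significant test, by itself, could not justify such a claim.

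**What to change.** 1. In SAP 6.14.6 and 6.14.7, report the estimated dose-minus-placebo difference in scale points with its one-sided 95% confidence limit in the harmful direction (upper for BPRS, lower for DSST). Take it from the same ANOVA, or from the bootstrap if 6.10 applies. Do this for each BPRS and DSST time point per dose, and for the pooled DSST model (Eq. 6).
2. State that a non-significant p-value is not reported as absence of effect.
3. Relabel the Table 7 safety null to match the no-worse wording of 6.3.

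This needs SAP wording and some extra table columns, with no new data, participants or models. The report will be slightly longer and less reassuring: with small cohorts the limits will be wide, and the report should show that.
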